8.1. Subject Disposition and Withdrawals

Subject disposition will be presented for all subjects in the Screening Set, which include the following:

- Number of subjects enrolled (i.e. signed Informed Consent)
- Number of screened, screen failures and reason for screen failure
- Number (%) of subjects randomized

Among the randomized subjects, the following will be summarized

- Number (%) of subjects in the Safety Set
- Number (%) of subjects in the Full Analysis Set
- Number (%) of subjects in the Per-Protocol Set
- Number (%) of subjects who completed the study through Week 16
- Number (%) of subjects who completed the study through Week 20
- Number (%) of subjects who discontinued treatment and their reason
- Number (%) of subjects who discontinued study prematurely and their reason

A separate by-subject listing of subject disposition and withdrawal will also be provided for the Screening Set. Subjects who screen failed will be included in this listing along with the reason for the screen failure.

Reasons for exclusion from analysis sets will be summarized in the Randomized Set and listed.

8.2. Protocol Deviations

All protocol deviations will be listed in the Randomized Set. Major protocol deviations will be summarized in the Randomized Set.

8.3. Demographic and Other Baseline Characteristics

Demographics and other baseline characteristics will be summarized for the Safety Set by actual treatment, for Randomized, Full Analysis, and Per Protocol Sets by randomized treatment and overall. Summary statistics and by-subject listings will be provided.

Demographics and baseline characteristics will include age, sex, ethnicity, race, weight, height, body mass index (BMI), age ≥ 85 (Y/N), age ≥ 65 and <85 years, with a medical history of asthma (Y/N), medical history of congestive heart failure (Y/N), medical history of Type 2 Diabetes Mellitus (Y/N), Clinical Frailty Scale score ≥ 4 (Y/N), Clinical Frailty Score (ordinal), receipt of current season influenza vaccine (Y/N) and each of the stratification levels (age ≥ 85 and clinical frailty score ≥ 4 ; age ≥ 85 and clinical frailty score < 4 ; $65 \leq$ age < 84 , clinical frailty score ≥ 4 and medical history of asthma; $65 \leq$ age

This document is confidential.

< 84, clinical frailty score ≥ 4 and no medical history of asthma; $65 \leq \text{age} < 84$, clinical frailty score < 4 and medical history of asthma; and $65 \leq \text{age} < 84$, clinical frailty score < 4 and no medical history of asthma).

Age at Screening = (Screening visit date - date of birth + 1) / 365.25 and truncated to complete years.

Height (in cm) = height (in inches) * 2.54

Weight (in kg) = weight (in lbs) * 0.4536

BMI (kg/m²) = Weight(kg)/[Height(m)²]

Similarly, baseline disease characteristics will be summarized for the Safety Set, Randomized, Full Analysis, and Per Protocol Sets.

By-subject listing of all demographic and baseline disease characteristic data will be provided for the Full Analysis Set.

8.4. Medical History and Concomitant Diseases

A summary table of the number and percentage of subjects by medical history, system organ class (SOC) and preferred term will be produced from the Safety Set. Medical history will be sorted alphabetically by SOC and in descending order of subjects per preferred term within each SOC.

Medical history will be coded using the Medical Dictionary for Regulatory Activities (MedDRA) version 22.0 or higher.

A separate by-subject listing of medical history will also be provided.

8.5. Medication

All prior and concomitant medications will be summarized based on classification using the Anatomical Therapeutic Chemical (ATC) classification and preferred drug name from the World Health Organization Drug Dictionary, version Mar 2019, or later.

A separate by-subject listing of medications will also be provided for the Safety Set.

8.5.1. Prior Medication

Prior medications are defined as medications entered in the eCRF that either start, or end before the first dose of study medication. Prior medications will be summarized by ATC level 2 and preferred drug name for the Safety Population.

Prior medications which continue after first dose of study medication will also be classified as a concomitant medication.

8.5.2. Concomitant Medication

Concomitant medications are defined as medication on the eCRF that are taken on, after, or are ongoing at the start date of dosing. Concomitant medications will be summarized by ATC level 2 and preferred drug name for the Safety Population.

This document is confidential.

9. Efficacy

9.1. Multiple Testing Strategy

A fixed sequence gate-keeping strategy will be used to control the study-wise error rate at a 2-sided α -level of 0.05. The following primary, secondary and exploratory efficacy endpoints will be tested in the sequence specified below:

Order	
H₁	The percentage of subjects with 1 or more CSRIs (with or without an associated laboratory-confirmed pathogen) beginning at least 3 days after the start of study drug treatment through Week 16.
H₂	The percentage of subjects with 1 or more CSRIs associated with ≥ 1 laboratory-confirmed pathogen(s) beginning at least 3 days after the start of study drug treatment through Week 16 as assessed by pre-specified clinical diagnostic criteria, and respiratory pathogen PCR of nasopharyngeal swabs, sputum gram stain and culture, and/or RIDTs.
H₃	The rate of CSRI (with or without an associated laboratory-confirmed pathogen) beginning at least 3 days after the start of study drug treatment through Week 16 as assessed by pre-specified clinical diagnostic criteria.
H₄	The rate of CSRIs associated with ≥ 1 laboratory-confirmed pathogen(s) beginning at least 3 days after the start of study drug treatment through Week 16 as assessed by pre-specified clinical diagnostic criteria and respiratory pathogen PCR of nasopharyngeal swabs, sputum gram stain and culture, and/or RIDTs.
H₅	The time to alleviation of moderate and severe respiratory illness symptoms due to CSRI beginning at least 3 days after the start of study drug treatment through Week 16.
H₆	The percentage of subjects with severe symptoms due to CSRIs beginning at least 3 days after the start of study drug treatment through Week 16.
H₇	The rate of all-cause hospitalizations beginning at least 3 days after the start of study drug treatment through Week 16.
H₈	The rate of UTIs beginning at least 3 days after the start of study drug treatment through Week 16 reported as adverse events
H₉	The percentage of subjects with 1 or more CSRIs (with or without an associated laboratory-confirmed pathogen) beginning at least 3 days after the start of study drug treatment through Week 20.

The primary endpoint, H₁, will be tested first at a 2-sided alpha level of 0.05. The subsequent endpoints will be tested in the order specified above also at a 2-sided 0.05 alpha-level of 0.05, if and only if the preceding endpoint was found to be statistically significant. If the preceding endpoint in the sequence fails to meet statistical significance, then testing of subsequent endpoints will be stopped and no further statistical conclusions will be made.

9.2. Estimands

This section presents a structured framework that link trial objectives with suitable and precise definition of how treatment effects are to be estimated. The estimand, which is the target of estimation to address

This document is confidential.

the scientific question of interest posed by the trial objective, with its 4 attributes as specified in the ICH E9(R1) Draft Addendum on Estimands and Sensitivity Analysis in Clinical Trials 2017, are provided below for the primary objective and key secondary objectives.

9.2.1. Primary Objective Estimand

The estimand used to address the primary objective “To determine if RTB101 as compared to placebo decreases the percentage of subjects with a CSRI (with or without an associated laboratory-confirmed pathogen) through Week 16” is defined by the following:

- Population:
 - Subjects in the FAS population
- Variable:
 - Occurrence of a CSRI, with or without an associated laboratory-confirmed pathogen, by the Week 16 visit
- Intercurrent events:
 - If a subject discontinues study prematurely due to an RTI AE or RTI SAE and the subject did not meet the definition of a CSRI, impute the subject experienced a CSRI
 - If a subject discontinues study prematurely for any reason other than an RTI AE or RTI SAE and the subject did not meet the definition of a CSRI, impute the subject did not have a CSRI
 - If a subject completed the study and has intermittent missing eDiary data and the subject did not meet the definition of a CSRI, impute the subject did not have a CSRI
- Population-level summary:
 - odds ratio, i.e. the ratio of the odds of having a CSRI in subjects treated with RTB101 compared to the odds of having a CSRI in subjects treated with placebo by the Week 16 visit

9.2.2. Secondary Objective Estimands

1. The estimand for the secondary objective “To determine if RTB101 as compared to placebo decreases the percentage of subjects with a CSRI associated with ≥ 1 laboratory-confirmed pathogen(s) through Week 16” is defined by the following:

- Population:
 - Subjects in FAS population
- Variable:
 - Occurrence of a CSRI with ≥ 1 laboratory-confirmed pathogen(s) by the Week 16 visit

This document is confidential.

- Intercurrent events:
 - If a subject discontinues study prematurely due to an RTI AE or RTI SAE and the subject did not meet the definition of a CSRI associated with ≥ 1 laboratory-confirmed pathogen(s), assume the subject experienced a CSRI with ≥ 1 laboratory-confirmed pathogen(s)
 - If a subject discontinues study prematurely for any reason other than an RTI AE or RTI SAE, and the subject did not meet the definition of a CSRI associated with ≥ 1 laboratory-confirmed pathogen(s), impute the subject did not have a CSRI with ≥ 1 laboratory-confirmed pathogen(s)
 - If a subject completed the study and has intermittent missing eDiary data and the subject did not meet the definition of a CSRI associated with ≥ 1 laboratory-confirmed pathogen(s), impute the subject did not have a CSRI with ≥ 1 laboratory-confirmed pathogen(s)
 - Population-level summary:
 - odds ratio, i.e. the ratio of the odds of having a CSRI with ≥ 1 laboratory-confirmed pathogen(s) in subjects treated with RTB101 compared to the odds of having a CSRI with ≥ 1 laboratory-confirmed pathogen(s) in subjects treated with placebo by the Week 16 visit
2. The estimand for the secondary objective “To determine if RTB101 as compared to placebo decreases the rate of CSRIs, with or without an associated laboratory-confirmed pathogen, through Week 16” is defined by the following:
- Population:
 - Subjects in FAS population
 - Variable:
 - Number of CSRIs with or without an associated laboratory-confirmed pathogen through the Week 16 visit
 - Intercurrent events:
 - If a subject discontinues study prematurely due to an RTI AE or RTI SAE and the subject did not meet the definition of a CSRI, assume the subject experienced one CSRI
 - If a subject discontinues study prematurely for any reason other than an RTI AE or RTI SAE and the subject did not meet the definition of a CSRI, impute the subject did not have a CSRI
 - If a subject completed the study and has intermittent missing eDiary data and the subject did not meet the definition of a CSRI, impute the subject did not have a CSRI
 - Population-level summary:

This document is confidential.

- rate ratio, i.e. the ratio of the rate of having a CSRI (with or without an associated laboratory-confirmed pathogen) in subjects treated with RTB101 compared to the rate of having a CSRI (with or without an associated laboratory-confirmed pathogen) in subjects treated with placebo by the Week 16 visit
3. The estimand for the secondary objective “To determine if RTB101 as compared to placebo decreases the rate of CSRIs associated with ≥ 1 laboratory-confirmed pathogen(s) through Week 16” is defined by the following:
- Population:
 - Subjects in FAS population
 - Variable:
 - Number of CSRIs with ≥ 1 laboratory-confirmed pathogen(s) through Week 16
 - Intercurrent events:
 - If a subject discontinues study prematurely due to an RTI AE or RTI SAE and the subject did not meet the definition of a CSRI associated with ≥ 1 laboratory-confirmed pathogen(s), assume the subject experienced one CSRI associated with ≥ 1 laboratory-confirmed pathogen(s)
 - If a subject discontinues study prematurely for any reason other than an RTI AE or RTI SAE, and the subject did not meet the definition of a CSRI associated with ≥ 1 laboratory-confirmed pathogen(s), impute the subject did not have a CSRI associated with ≥ 1 laboratory-confirmed pathogen(s)
 - If a subject completed the study and has intermittent missing eDiary data and the subject did not meet the definition of a CSRI associated with ≥ 1 laboratory-confirmed pathogen(s), impute the subject did not have a CSRI associated with ≥ 1 laboratory-confirmed pathogen(s)
 - Population-level summary:
 - rate ratio, i.e. the ratio of the rate of having a CSRI with ≥ 1 laboratory-confirmed pathogen(s) in subjects treated with RTB101 compared to the rate of having a CSRI with ≥ 1 laboratory-confirmed pathogen(s) in subjects treated with placebo by the Week 16 visit
4. The estimand for the secondary objective “To determine if RTB101 as compared to placebo decreases the percentage of subjects with severe symptoms due to clinically symptomatic respiratory illnesses through Week 16” is defined by the following:
- Population:
 - Subjects in FAS population
 - Variable:

This document is confidential.

- Occurrence a CSRI with severe symptoms by the Week 16 visit
 - Intercurrent events:
 - If a subject discontinues study prematurely due to an RTI AE or RTI SAE and the subject did not meet the definition of a CSRI with severe symptoms, assume the subject experienced a CSRI with severe symptoms
 - If a subject discontinues study prematurely for any reason other than an RTI AE or RTI SAE and the subject did not meet the definition of a CSRI with severe symptoms, impute the subject did not have a CSRI with severe symptoms
 - If a subject completed the study, has intermittent missing eDiary data and the subject did not meet the definition of a CSRI with severe symptoms, impute the subject did not have a CSRI with severe symptoms
 - Population-level summary:
 - odds ratio, i.e. the ratio of the odds of having a CSRI with severe symptoms in subjects treated with RTB101 compared to the odds of having a CSRI with severe symptoms in subjects treated with placebo by the Week 16 visit
5. The estimand for the secondary objective “To determine if RTB101 as compared to placebo decreases time to alleviation of moderate and severe respiratory illness symptoms through Week 16” is defined by the following:
- Population:
 - Subjects in FAS population
 - Variable:
 - Time to alleviation of moderate and severe CSRI symptoms
 - Intercurrent events:
 - If a subject discontinues study prematurely due to an RTI AE or RTI SAE and time to alleviation of moderate and severe respiratory illness symptoms has not been reached, subject is censored on the date of last eDiary entry
 - If a subject discontinues study prematurely for any other reason than an RTI AE or RTI SAE and time to alleviation of moderate and severe respiratory illness symptoms has not been reached, subject is censored on the date of last eDiary entry
 - If a subject completed the study and has intermittent missing eDiary data and time to alleviation of moderate and severe respiratory illness symptoms has not been reached, subject is censored on the date of last eDiary entry
 - Population-level summary:

This document is confidential.

- hazard ratio, i.e. the hazard rate of alleviation of moderate and severe respiratory illness symptoms in subjects treated with RTB101 divided by the hazard rate of alleviation of moderate and severe respiratory illness symptoms in subjects treated with placebo by the Week 16 visit

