⁶ All subjects will be screened for Hepatitis B surface antigen (HBsAg), Hepatitis C and HIV. Screening for Hepatitis C will be based on HCV antibodies and if positive, HCV RNA levels should be determined. Evaluation for HIV seropositivity will be performed, and, if positive, confirmation by a second technique available at the laboratory study site (e.g., Western blot) should be performed.

⁷ Clinical Frailty Scale score should be entered into IXRS prior to assignment of randomization code.

⁸ Subjects who prematurely discontinue study treatment due to an AE should return to the study site as soon as possible for an unscheduled visit to return all study drug for reconciliation and accountability, and to perform the following assessments: Vital signs, Complete Physical Exam, Hematology, Chemistry and Urinalysis. Subjects who discontinue due to a clinically symptomatic respiratory illness AE should also undergo respiratory illness assessments such as nasopharyngeal swab collection if not already done. Subjects who discontinue treatment for reasons other than an AE should return at the next scheduled visit at which time they will return all study drug for reconciliation and accountability at the next scheduled study visit.

⁹ Study drug is dispensed at Day 0, Week 4, Week 8, and Week 12 (however, in the case of lost or damaged study drug, study drug can be dispensed at any study site visit). At Weeks 4, 8 and 12, subjects will return study drug and will be dispensed new bottles.

^{10a} Subjects will not return or be dispensed new study drug at these visits. Subjects will just bring their supply of study drug to the study site for pill count for compliance and then will return home with the same supply of study drug.

^{10b} At visit Week 16 or premature study discontinuation (PSD), all study drug will be returned, and the final study drug accountability will be performed. All subjects will self-administer study drug at home on the morning of their Week 16 visit.

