6.7.2. Laboratory-Confirmed Clinically Symptomatic Respiratory Illness

When a subject reports symptoms of a respiratory illness in which at least one unique respiratory symptom (runny nose, sneezing, stuffy nose, sore throat, hoarseness, or cough) is reported on 2 consecutive entries in their eDiary, the sites will contact the subject and instruct the subject to come to the study site if they are able to within 48 hours for evaluation and to obtain a nasopharyngeal swab. Subjects should only have one nasopharyngeal swab obtained during each episode of a respiratory illness. Please refer to the SOM for more details. Laboratory confirmation of clinically symptomatic respiratory illness will be obtained using three methods:

- The FILMARRAY Respiratory panel polymerase chain reaction (PCR) Assay of nasopharyngeal swabs in all subjects
- Sputum gram stain and culture obtained in subjects with a productive cough that is new or a change from their normal baseline
- RIDT obtained in subjects with influenza-like illness symptoms (such as 1 or more respiratory symptom (cough, sore throat or nasal symptoms) and 1 or more constitutional symptom (such as body aches or feverishness/chills)).

Subjects who are unwilling or unable to come to the study site for an unscheduled visit should have the nasopharyngeal swab (and sputum specimen or RIDT , if indicated) obtained at a home visit by trained personnel. All subjects with influenza-like illness who have influenza detected by RIDT or nasopharyngeal swab PCR should receive anti-influenza treatment per local standard of care, unless contraindicated, and/or other appropriate medical care.

Study drug treatment can be continued in subjects who require antibiotics or anti-influenza treatment for treatment of an RTI.

Laboratory-confirmed clinically symptomatic respiratory illness will be defined programmatically as a symptomatic respiratory illness that meets the prespecified clinical diagnostic criteria outlined in [Section 6.7.1](#) and is associated with a laboratory-confirmed pathogen detected by one or more of the 3 methods described above. Further details will be provided in the SAP.

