9.4. Analyses of Secondary Efficacy Endpoints

9.4.1. Percentage of Subjects with One or More Clinically Symptomatic Respiratory Illnesses Associated with ≥ 1 Laboratory-confirmed Pathogen(s)

The percentage of subjects with CSRI associated with ≥ 1 laboratory-confirmed pathogen(s) beginning at least 3 days after the start of study drug treatment through Week 16 (H_2) as assessed by pre-specified clinical diagnostic criteria and respiratory pathogen PCR of nasopharyngeal swabs, sputum gram stain and culture, and/or RIDTs will be analyzed in the same manner as the primary efficacy analysis as described in 9.3.1 based on the estimand for the secondary objective corresponding to this endpoint described in 9.2.2 above.

Laboratory results from a specimen obtained within 3 days before the CSRI start date through the CSRI end date will be used to determine if the CSRI is associated with ≥ 1 laboratory-confirmed pathogen. Laboratory confirmation includes a positive respiratory pathogen PCR of nasopharyngeal swabs, sputum gram stain and culture, and/or RIDT. If multiple specimens are obtained for a particular CSRI, then any positive result will be counted as laboratory confirmation if it occurs within 3 days before the CSRI start date through the CSRI end date. A laboratory-confirmed CSRI may be associated with multiple pathogens. Note that organisms considered to identify a positive sputum specimen should meet standard microbiological laboratory criteria of growing from a sputum specimen with > 25 WBC/hpf and < 10 Squamous cells/ hpf, and they have matching morphology on gram stain and culture.

Summary statistics will be presented along with a full data listing by treatment group.

9.4.2. Rate of Clinically Symptomatic Respiratory Illnesses (with or without an Associated Laboratory-confirmed Pathogen)

The rate of CSRI (with or without an associated laboratory-confirmed pathogen) beginning at least 3 days after the start of study drug treatment through Week 16 (H_3) will be analyzed based on the negative binomial distribution. The first 3 days of study drug treatment will not be included in determining the denominator of rate.

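### In H2 and H4, a subject who leaves the study because of an RTI is counted as having a laboratory-confirmed CSRI even if the specimen for that illness tested negative

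*SAP*

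**What the plan says.** SAP 9.2.2 lists rules for intercurrent events under each secondary estimand. For a subject who leaves the study early because of an RTI AE or SAE:

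- Item 1 (H2, percentage with a laboratory-confirmed CSRI): a subject who "did not meet the definition of a CSRI associated with ≥ 1 laboratory-confirmed pathogen(s), assume the subject experienced a CSRI with" at least one laboratory-confirmed pathogen.
- Item 3 (H4, rate of laboratory-confirmed CSRIs): "assume the subject experienced one CSRI associated with" at least one laboratory-confirmed pathogen.

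SAP 9.4.1 and 9.4.3 run H2 and H4 "based on the estimand for the secondary objective corresponding to this endpoint described in 9.2.2 above", so these rules govern the tested analyses.

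Confirmation itself is a matter of a positive test. SAP 9.4.1 states: "Laboratory confirmation includes a positive respiratory pathogen PCR of nasopharyngeal swabs, sputum gram stain and culture, and/or RIDT". The specimen window is also given there: "Laboratory results from a specimen obtained within 3 days before the CSRI start date through the CSRI end date will be used". Protocol 6.7.2 agrees: the illness must meet the clinical criteria and it "is associated with a laboratory-confirmed pathogen detected by one or more of the 3 methods described above".

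**The concern.** The imputation depends on two facts only: the subject left the study because of an RTI, and the subject had not met the laboratory-confirmed definition. There are two quite different ways of not meeting it. Either no specimen was tested, which is missing data, or a specimen was tested and no pathogen was found, which is an observation. The rule treats both as an event.

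Protocol 3.2 says the laboratory-confirmed endpoint is there to show the drug's effect on illness proven to have an infectious cause. Counting an illness with a negative test does not serve that purpose. H2 stands second in the fixed sequence of SAP 9.1, so its result also decides whether H3 to H9 are tested at all.

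**Working it through.** **Tracing the rule.** Take a subject who meets the clinical CSRI criteria, has one valid specimen in the window, tests negative, and has no other laboratory-confirmed CSRI. The SAP 9.2.2 item 1 rules give:

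| What the subject does next | H2 score |
|---|---|
| Completes the study | no event |
| Leaves for a reason other than an RTI AE/SAE | no event |
| Leaves because of an RTI AE/SAE | event |

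The laboratory finding is the same in all three rows. Neither document makes an exception for a tested-negative specimen.

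**Can a negative result be on file?** Yes. Protocol 3.1 and 6.7.2 call subjects in for a swab, or arrange a home visit, after a respiratory symptom on two consecutive diary entries. Protocol Table 6-1, footnote 8, adds: "Subjects who discontinue due to a clinically symptomatic respiratory illness AE should also undergo respiratory illness assessments such as nasopharyngeal swab collection if not already" (that is, unless a swab was taken before). That footnote is written for stopping treatment, so it shows only that such results can exist.

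**Is the rule tested anywhere?** No. The tipping-point analyses in SAP 9.3.2.1 cover only the primary endpoint and keep RTI withdrawals as events. SAP 9.6.1 and 9.6.2 add mid-turbinate swabs and leave this rule alone.

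**Size.** The plan gives no figure on this point: no H2 event rate, no count of RTI-related study withdrawals, no proportion testing negative. Its one design figure is the sample size for H1, which reproduces: 28.2% vs 19.7%, 533 per arm, two-sided 0.05 gives likelihood-ratio power 0.903 against the stated 90%.

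For H2, assume 80 placebo and 57 RTB101 events of 533 per arm (15.0% and 10.7%). The unadjusted likelihood-ratio statistic is G = 2 Σ O ln(O/E) on 1 degree of freedom. In the starting case the expected counts are 68.5 events and 464.5 non-events in each arm:

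G = 2[80 ln(80/68.5) + 453 ln(453/464.5) + 57 ln(57/68.5) + 476 ln(476/464.5)] = 24.831 − 22.713 − 20.951 + 23.282 = 4.449, p = 0.035.

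| Imputed events added | Placebo vs RTB101 | G | p |
|---|---|---|---|
| none | 80 vs 57 | 4.449 | 0.035 |
| 1 placebo | 81 vs 57 | 4.816 | 0.028 |
| 1 in each arm | 81 vs 58 | 4.394 | 0.036 |
| 3 in each arm | 83 vs 60 | 4.289 | 0.038 |
| 1 RTB101 | 80 vs 58 | 4.044 | 0.044 |

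None of these crosses 0.05. A single event matters only near the threshold: 78 vs 57 gives p = 0.053 and 79 vs 57 gives 0.043.

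**Range over the assumed placebo rate.** Assume a true 30% relative reduction and add k/533 to each arm's rate. Power = Φ[(d − 1.96·SE₀)/SE₁], where d is the difference in rates and SE₀ and SE₁ are the pooled and unpooled standard errors. For 15% vs 10.5%: (0.045 − 1.96 × 0.02043)/0.02038 = 0.243, so power is 0.596.

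| Placebo rate | No imputed events: RR, power | 5 in each arm: RR, power | 5 placebo, 3 RTB101: RR, power |
|---|---|---|---|
| 10% | 0.700, 0.419 | 0.726, 0.388 | 0.691, 0.477 |
| 15% | 0.700, 0.596 | 0.718, 0.571 | 0.694, 0.644 |
| 20% | 0.700, 0.742 | 0.713, 0.724 | 0.696, 0.778 |

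Equal additions dilute the effect. Additions weighted to placebo strengthen it. For scale, the Phase 2b combined missing-data rate of 5.1% (Protocol 9.4.2) would be about 0.051 × 533 = 27 subjects per arm. Only part of these would have left because of an RTI, and fewer still would have a negative test.

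**The case against.** The best defence is that this is a prespecified rule for an intercurrent event. It works like a composite strategy: leaving the study because of an RTI is a bad outcome and is scored as one. H2 is a subject-level outcome through Week 16, so one negative swab does not settle the status of someone who left earlier. Protocol 3.2 admits that the assays miss some pathogens, and only one nasopharyngeal swab is taken per episode. Overriding recorded data is also not peculiar to H2 and H4: the severe-symptom estimand (item 4) has the same form.

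Part of this stands. The rule is a choice and not a coding error, and a negative swab is not proof of no infection. But the variable in items 1 and 3 is laboratory-confirmed CSRI alone, not a composite with withdrawal. Shortened follow-up cannot justify the rule, because subjects who leave for other reasons are also cut short and are scored as having no event. Protocol 3.2 uses undetected pathogens as the reason for counting illness with or without a pathogen in H1. That argument does not carry over to an endpoint defined by detection.

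It is also fair that very few subjects may qualify. Study drug can continue through an RTI (Protocol 6.7.2). Those who stop drug are expected to stay in follow-up (Protocol 5.5.2). Withdrawal of consent, as defined in Protocol 5.5.3, includes refusing analysis of material already obtained.

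Two stronger readings are tempting. A reader might infer that the rule was copied from H1, where it merely fills in missing diary data. No document says so, and the H1 rule in SAP 9.2.1 does not require any diary data to be missing. A reader might also infer that the rule favours RTB101, because RTI withdrawals would gather on placebo if the drug works. That can happen, but the documents give no counts by arm, and equal numbers in each arm move the risk ratio towards 1.

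**Conclusion.** The point holds as a matter of definition. As written, H2 and H4 count as laboratory-confirmed an illness whose specimen was tested and negative, if the subject left the study because of an RTI. This follows from the lack of any exception; the SAP does not say in words that a negative result is to be overridden. The conflict is with the endpoint's own purpose, and no planned analysis would show its effect.

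The consequence is probably small. H1 is unaffected, stopping drug does not trigger the rule, and a subject who already had a laboratory-confirmed CSRI is untouched. Direction and size are unknown. The p-values rest on assumed counts of 80 and 57 and on an unadjusted test, whereas the plan uses a covariate-adjusted logistic model for H2. They show sensitivity to single events and do not forecast bias. This is a minor improvement, worth making before unblinding so that the choice cannot look driven by the result.

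**What to change.** In SAP 9.2.2 items 1 and 3, for subjects who leave the study because of an RTI AE or SAE without having met the laboratory-confirmed definition:

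- Impute a laboratory-confirmed event only if no valid specimen was obtained for that illness.
- Define the window as 3 days before onset through the end of the illness or study exit, whichever applies. Onset is the CSRI start date, or the RTI AE start date if the CSRI criteria were never met. The second case needs stating because the window in SAP 9.4.1 is tied to CSRI dates that such a subject does not have.
- If a valid specimen was negative, score no laboratory-confirmed event for that illness. If it was positive, keep the imputed event.
- Report the current rule as a sensitivity analysis for H2 and H4.

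The cost is a short SAP paragraph, a definition of a valid specimen, and one extra run for each of the two endpoints. No new data are needed. The small downside is that a false-negative test in such a subject is scored as a non-event, as it already is for subjects who complete the study.
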